7.1.5 Clinical Laboratory Tests

Hematology and serum chemistries, including basic metabolic panels, liver function testing, complete blood counts, and platelet levels will be performed as part of the participant's standard medical care at clinical care laboratories at the treating site. Five milliliters of blood for special laboratory measurements, including serum citrulline and arginine levels will be collected at each of the scheduled time points (see Appendix A) separated into plasma and cellular components and frozen at -70°C. These samples will be thawed, and the variables measured, all at the same time, after all enrolled participants have completed the study. Citrulline and arginine will be measured using a Beckman 7300 Amino Acid Analyzer or equivalent. Safety labs, including complete blood count, complete platelet count, basic metabolic panel, and liver function tests, will be performed as part of the participant's standard medical care at clinical care laboratories at the treating site.

Five milliliters of blood will be collected in an EDTA anti-coagulated tube at hours 0, 2, 12, and every 2 days until extubation for a maximum of 10 days- i.e. days 1 (hours 0, 2, 12) then on days 2, 4, 6, 8, and 10. Plasma will be centrifuged and the supernatant and cellular portions will be frozen at -70°C.

7.1.6 Pregnancy

Female participants of childbearing potential must have a negative urine or serum HCG pregnancy test to be eligible for the study.

7.2 Schedule of Observations and Procedures

The schedule for all study related procedures and evaluations is summarized in Appendix A.

7.2.1 Baseline Assessments

Eligibility of participants will be assessed based on the inclusion and exclusion criteria. Prior to initiation of study drug infusion (defined as study time=0 hours), baseline safety assessments, including complete blood and platelet counts, measures of renal and liver function, and metabolic panel, will be collected from the medical record. Measurements within 36 hours prior to starting study infusion will be considered appropriate for baseline measurements. In cases where more than one measurement is available in that 36 hours, the measurements closest to the start of study infusion will be used. Blood for baseline plasma citrulline and arginine will be drawn as close to time=0 as possible. Baseline hemodynamic measurements (i.e. MAP and vasopressor dosage) will be taken within 15 minutes prior to initiation of study material.

7.2.2 On Study (days 0-DC) Assessments

Study drug administration should begin as soon as possible after confirming the participant meets the eligibility criteria. Time=0 hours is defined as the time when study infusion is initiated. All times are calculated in relation to the time study drug was initiated at Hour 0. The study infusion will last for a maximum of 10 days.

MAP will be measured per hospital unit or ICU protocol during the entirety of the infusion. MAP and if required vasopressor dosages will be recorded in the CRF 2 and 12 hours after start of study infusion and as close as possible to 8AM on study days one through 10. VDI will also be calculated for these timepoints.

Blood samples for plasma citrulline, arginine measurements will be collected as close to 8AM as possible on study days 2, 4, 6, 8, and 10, after Hours 0, 2, 12 are completed. All of these specimens will be centrifuged, and the supernatant and cellular portions frozen at -70°C for subsequent batch analysis of all specimens once all participants have completed the study.

Patients will discontinue study drug on Day 10. Patients will continue to have all procedures in the schedule of procedures except for screening procedures, study drug, and blood draw for plasma citrulline.

Patients who complete study visit day 11 will continue to be followed from day 12 to discharge. From day 12 to discharge the following values will continue to be collected during this time are vital signs, hospital status, ICU status, and non-invasive and invasive ventilator settings. A further follow up will occur on D28 and D60 as a telephone visit, if discharged earlier.

Concomitant medications and adverse event monitoring will be performed and reported in CRFs.

See the Schedule of Procedures in Appendix A for further details.

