5.1.2 Study Assessments

The assessment of efficacy will include collection of plasma for analysis of citrulline and arginine levels at day 1 hours 0, 2, 12, and the alternating morning of study days the infusion is running for a maximum of 10 days, i.e., on days 2, 4, 6, 8 and 10. A patient will exit the study early if they have been weaned off all oxygen support before 10 days. Additional efficacy measures will include clinical outcomes, including progression of acute lung injury and lengths of hospital and ICU stay.

The assessment of safety will include collection of hemodynamic measurements at least every 4 hours on a hospital unit and--if a patient is critically ill in an ICU--hourly while the study material is infusing and for 12 hours after completion of the infusion in each patient. Hemodynamic measurements will be converted to a vasopressor dependency index for analysis if a patient becomes critically ill. Adverse event reporting will also serve as a means of safety analysis. Additional safety measures will be biochemical and hematologic laboratory measurements. The biochemical laboratory measurements, including liver function tests (ALT, AST, bilirubin, alkaline phosphatase), kidney function tests, and electrolytes, along with hematologic laboratory measurements, including complete blood count and platelet count, will be collected when available for any study day in order to evaluate for adverse events.

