7.1.3 Hemodynamic Assessments

Blood pressure measurements will represent a major component of the hemodynamic assessments. Vasopressor dosages in critically ill patients will also form a significant component of these assessments. Vasopressor Dependency Index (VDI) will be used as the measure of hemodynamic assessment. VDI is a continuous variable calculated by dividing vasopressor index (summation of all pressors) by MAP. VDI will be calculated at baseline (immediately before start of the infusion), again 2 hours after completion of the bolus, and every 4 hours during the infusion. Any cases where the VDI increases by more than 20% from baseline will result in interruption of the study infusion and review by the safety officer in an expedited fashion.

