10.5 Primary Endpoints

Time to an intubation event in hours from the start of the study drug infusion or overall duration of mechanical ventilation will represent the primary clinical endpoint. The number of patients starting intubation over time will be displayed in the form of survival curves using the Kaplan-Meier method and analyzed using a two-sided log-rank test. Statistical significance will be claimed if the computed p-value is equal to or less than 0.05.

Citrulline and arginine plasma levels will represent the primary biochemical endpoint of this study. A 5 mL sample of blood will be obtained for amino acid analysis at hour 0 before study medication is administered, 2 and 12 hours after the bolus and as close as possible to 8 AM on days 2, 4, 6, 8, and 10. Samples will be collected in citrated tubes and placed on ice until they can be centrifuged. Plasma and cellular components will be frozen at -70 °C until batch analysis. Concentrations of citrulline, arginine, and ornithine will be measured in the plasma samples using cation-exchange chromatography with a Beckman 7300 amino acid analyzer or equivalent. The analysis team will provide the means and standard

deviations for citrulline, arginine, and ornithine plasma levels separately for each treatment group. A generalized linear mixed model (GLMM) with appropriate link function (i.e., identity link for continuous outcome) will be used to compare these plasma amino levels across the two intervention groups. The model will examine how the treatment means differ (i.e., main treatment effect), how treatment means change over time (i.e., main time effect), and how differences between treatment means change over time (i.e., treatment-by-time effect).

The primary safety outcome will be worst VDI any time after start of infusion. VDI is a continuous variable calculated by dividing vasopressor index (summation of all pressors) by MAP. VDI will be calculated at baseline (immediately before start of the infusion), 2 hours after completion of the bolus, and every 4 hours during the infusion. Worst VDI will be compared between groups using ANCOVA analysis with the baseline VDI as the covariate.

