The risks of citrulline are theoretical. In previous studies enrolling hundreds of humans, no serious adverse events have been attributed to either oral or intravenous citrulline. Citrulline may increase NO production and exacerbate hypotension. Arginine, a product of citrulline via the urea cycle, has been reported to exacerbate hypotension. The blood pressure of every participant in this study will be monitored closely throughout the study and especially during the infusion. As these patients will be cared for in a hospital unit or ICU, blood pressure measurements will be taken per hospital unit or ICU protocol. Hypotension, as measured by vasopressor dependency index (VDI) represents an *a priori* endpoint of the study. VDI will be calculated 2 hours after the bolus and daily. Any worsening of VDI by 33% or more will prompt review by the safety monitor. Although it is likely to reduce organ dysfunction by attenuating inflammation and oxidative stress, daily labs will be monitored for adverse events on organ functioning. The citrulline will be administered in a small volume of 5% dextrose water (30 mL bolus followed by ~15 mL/hr). This small amount of dextrose should not dramatically increase blood sugar levels in these patients and as such, should pose minimal risk. Furthermore, any event which the investigator or primary team is concerned may be related to study drug administration will be reported as an adverse event. Participants will be monitored for any signs of allergic reaction, including new wheezing, itching and/or rash. Blood pressure, which might fall during severe allergic reactions such as anaphylaxis, will be closely monitored in the hospital or ICU setting with treatment available as needed.

The placebo will be a small volume of 5% dextrose water (30 mL bolus followed by ~15 mL/hr). Although administration of dextrose in theory could raise blood sugar levels, the small volume will result in little dextrose being administered which should not significantly increase blood sugar levels in these patients and as such, should pose minimal risk. In addition, blood sugar levels are routinely measured and monitored closely as part of routine care in intensive care unit patients, especially those with severe sepsis.

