APPENDIX A: Schedule of Events

Measurement	Day 0 (baseline)	Day 1	Day 2	Day 3	Day 4	Day 5	Day 6	Day 7	Day 8	Day 9	Day 10	Day 11	Day 12-DC	Day 28 ^e Follow-up	Day 60 ^e Follow-up
Informed Consent	X														
Demographics- Hx & Px	X														
Eligibility Assessment	X														
Pregnancy Test	Xc														
Study Drug Administration		X	X	X	X	X	X	X	X	X					
Vital Signs		X	X	X	X	X	X	X	X	X	X	X	X		
Mean Arterial Pressure		Xa,b,d	X	X	X	X	X	X	X	X	X	X			
Vasopressor Dosages		Xa,b,d	X	X	X	X	X	X	X	X	X	X			
Basic Metabolic Panel		A	A	A	A	A	A	A	A	A	A	A			
CBC		A	A	A	A	A	A	A	A	A	A	A			
LFTs		Ab	A	A	A	A	A	A	A	A	A	A			
D-dimer blood draw		Xa,b	X		X		X		X		X		X		
CRP		Xa,b	X		X		X		X		X		X		
5 ml blood for citrulline etc.		Xa,b	X		X		X		X		X				
SaO2/ FiO2 ratio		X	X	X	X	X	X	X	X	X	X	X			
PaO2		X	X	X	X	X	X	X	X	X	X	X			
ABG		A	A	A	A	A	A	A	A	A	A	A			
Hospital status		X	X	X	X	X	X	X	X	X	X	X	X	X	X
ICU status		X	X	X	X	X	X	X	X	X	X	X	X	X	X
Non-invasive ventilation status		X	X	X	X	X	X	X	X	X	X	X			
Invasive ventilation status		X	X	X	X	X	X	X	X	X	X	X			
ConMed Review		X	X	X	X	X	X	X	X	X	X	X	X	X	X

Adverse Event Review		X	X	X	X	X	X	X	X	X	X	X	X	X	X	X
----------------------	--	---	---	---	---	---	---	---	---	---	---	---	---	---	---	---

a= measurement should be recorded or performed at hours 0, 2 and 12

b= Day 1 hour 0 samples/procedure must be collected/recorded before study drug is administered.

c= only perform if patient is of childbearing potential

d= must be collected 15 minutes prior to administration of study medication

e= Day 28 and Day 60 are telephone follow ups

X= Study Procedure A= Standard of Care

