### **Statistical Method for the Safety Endpoint (Hemodynamic status)**

The vasopressor dependency index (VDI) is a continuous variable calculated by dividing vasopressor index (summation of all pressors) by the mean arterial blood pressure (MAP). VDI will be calculated at baseline (immediately before start of the infusion), 2 hours after completion of the bolus, and every 4 hours during the infusion. We will report descriptive statistics (mean  $\pm$  SD) of baseline and worst VDI separately for each treatment group. Worst VDI will be compared between groups using an analysis of covariance (ANCOVA) with the baseline VDI as the covariate.

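### Worst VDI is defined on 4-hourly values, but the only stated CRF rule records its components at hours 0, 2 and 12 and once a day, and nothing says which readings feed the endpoint

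*Protocol*

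**What the plan says.** **Definition.** Protocol 10.5: "The primary safety outcome will be worst VDI any time after start of infusion". VDI is the summed vasopressor index divided by MAP. Protocol 7.1.3 calculates it at baseline, "again 2 hours after completion of the bolus, and every 4 hours during the infusion". Section 10.5 and the SAP method for hemodynamic status give the same times (SAP: "2 hours after completion of the bolus, and every 4 hours during the infusion"). Protocol 9.3 is also 4-hourly, but puts the first value 60 minutes after the bolus.

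**Recording.** Protocol 7.2.2 has MAP and any vasopressor doses "recorded in the CRF 2 and 12 hours after start of study infusion and as close as possible to 8AM on study days" (days 1-10), and says VDI is calculated for those times as well. For MAP and vasopressor dosages, Appendix A carries the Day 1 footnote "a= measurement should be recorded or performed at hours 0, 2 and 12", then a single mark per day through Day 11. Protocol 11.5, which does not mention the CRF, says: "VDI will be calculated 2 hours after the bolus and daily".

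**Bedside measurement.** Protocol 5.1.2: "The assessment of safety will include collection of hemodynamic measurements at least every 4 hours on a hospital unit", hourly for critically ill patients in the ICU, and for 12 hours after the infusion. These are to be converted to VDI for analysis if the patient becomes critically ill. The SAP's Study Assessments section repeats this.

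**Status.** The protocol names worst VDI through day 10 as its primary safety variable. The SAP lists it under secondary safety endpoints, although SAP Table 2 keeps the primary label.

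**The concern.** A maximum depends on how often one looks. The definition implies six values a day, and the CRF rule supplies one a day after Day 1. Two people following these documents, one working from the SAP method and one from the CRF schedule, could compute different values of the same safety variable for the same patient.

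This matters more here than in many trials. Protocol 11.4 plans no data safety monitoring board, and the one planned group safety review, after 20 patients (Protocol 10.7), looks at VDI and hypotension. Patients enter unintubated on the floor, so vasopressor use may be confined to a minority (an inference; the documents give no rate). For a patient with a single short episode, a missed reading turns a positive worst VDI into zero.

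**Working it through.** The documents give no sample size, power or distribution for VDI, so there is no planned figure to reproduce. The check compares the schedules and counts what each delivers.

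**1. Schedules side by side**

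| Place | VDI or component times after baseline |
|---|---|
| Protocol 7.1.3, 10.5; SAP hemodynamic method | 2 h after bolus, then every 4 h during infusion |
| Protocol 9.3 | 60 min after bolus, then every 4 h during infusion |
| Protocol 11.5 | 2 h after bolus, then daily |
| Protocol 7.2.2 (CRF) | 2 h, 12 h, about 8AM on days 1-10 |
| Protocol Appendix A | 2 h and 12 h on Day 1, then once daily |

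**2. Route to the analysis.** Protocol 12.2 records data on CRFs and then enters them in the database; 12.4 names Medrio as the capture tool; the SAP's data handling section analyses SAS extracts transferred under the Medrio procedure. The only CRF rule for MAP and vasopressor doses is in 7.2.2. The SAP's timeline section also points to Appendix A (citing protocol version 2.0), so the SAP itself refers to both schedules.

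**3. Number of readings (maximum infusion 10 days = 240 h)**

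- 4-hourly definition: 240/4 = 60, plus hour 2 = 61.
- CRF rule: hours 2 and 12 plus ten 8AM readings = 12, or 11 if an 8AM reading falls at hour 12.
- Share: 11/61 = 18%; 12/61 = 20%.
- 4-day infusion: 96/4 + 1 = 25, against 5 or 6. 2-day infusion: 48/4 + 1 = 13, against 3 or 4.

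**4. Chance of sampling a rise lasting L hours.** Assumptions: onset uniform over 0 to 240 - L, and infusion started at 14:00, so the CRF times are hours 2, 12, 18, 42, ..., 234. A rise is sampled if a reading falls inside it. The probability is the length of the union of the intervals [t - L, t], cut to the onset range, divided by 240 - L.

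- L = 4: (2 + 4 + 10×4)/236 = 46/236 = 19.5%
- L = 6: (2 + 6 + 10×6)/234 = 68/234 = 29.1%
- L = 8: (2 + 8 + 6 + 8×8 + 6)/232 = 86/232 = 37.1%
- L = 12: (12 + 6 + 8×12 + 6)/228 = 120/228 = 52.6%
- L = 24: 100%

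A simulation of 100,000 onsets gave 19.5%, 29.4%, 37.0%, 52.7% and 100%. The 4-hourly rule samples every rise of 4 h or more. For rises of 1 h and 2 h it samples 24.8% and 50.6%, against 5.0% and 10.1% at the CRF times.

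**5. How far the two maxima differ.** In a stationary first-order autoregressive simulation (20,000 patients, standard normal scale, correlation between values 4 h apart assumed from 0 to 0.95), the highest 4-hourly value falls at the point nearest a CRF time in about 20-21% of patients throughout.

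| 4-h correlation | Mean 4-hourly maximum (SD units) | Mean CRF maximum (SD units) | Correlation of the two maxima |
|---|---|---|---|
| 0 | 2.33 | 1.63 | 0.06 |
| 0.8 | 2.01 | 1.55 | 0.73 |
| 0.95 | 1.43 | 1.19 | 0.95 |

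The 0.06 partly reflects 8AM readings falling between 4-hourly times under the assumed start.

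**The case against.** The strongest reply is that the data exist. Protocol 5.1.2 and the SAP's Study Assessments section call for 4-hourly or hourly measurements and their conversion to VDI for analysis. Protocol 9.3 says cardiovascular function is collected systematically as MAP and vasopressor dose. Protocol 12.1 names chart abstraction as a main source. The sentence in 7.2.2 on VDI can be read as adding time points to the 4-hourly series. Hypotension is also collected as an adverse event (9.1) and is part of the 20-patient review.

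This stands against a stronger reading. A reader might infer that peaks are never captured; the documents do not support that, because the readings are taken and charted. The reply does not close the gap: no section carries those readings to the CRF, and chart abstraction is named without any VDI rule.

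Two further inferences also fail:

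- *That the CRF rule causes the absence of a value in the first 2 hours after the bolus.* The 4-hourly definition in 7.1.3, 10.5 and the SAP also starts at 2 hours. The real conflict is with the 60-minute value in 9.3.
- *That readings stop when the infusion is interrupted.* Only the 4-hourly frequency is tied to the infusion. Section 7.2.2 and Appendix A record daily without that condition, and 11.5 continues data collection when drug is stopped early because oxygen is no longer needed.

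It is also fair to say that the SAP places the variable among secondary safety endpoints, which lowers its formal rank but does not change how it is computed.

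**Conclusion.** The inconsistency holds. The stated recording rule does not deliver the series on which the stated safety variable is defined, and neither document names the readings that feed worst VDI.

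The count of 11-12 against 61 follows from the documents for a full 10-day infusion. The direction is also certain: a maximum over the CRF times cannot exceed the worst value at any time after the start of infusion, which is how Protocol 10.5 words the outcome. The sampling percentages rest on assumed random onset and a 14:00 start. Short rises are usually missed, rises of about 12 hours are caught roughly half the time, and rises of 24 hours or more are always seen.

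A reader might go on to conclude that any hemodynamic harm would be diluted by a known amount. The documents do not support that. The loss may be small if VDI is highly persistent and large if it is not, the documents give no basis for choosing, and a lower value in both arms does not by itself fix the effect on their difference.

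The 60-minute versus 2-hour first value is a separate conflict that must be reconciled.

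**What to change.** Reconcile Protocol 7.1.3, 7.2.2, 9.3, 10.5, 11.5 and Appendix A, and the SAP method for hemodynamic status, to one VDI data-collection schedule, including the time of the first post-bolus value.

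Enter in the CRF the MAP and vasopressor doses from the 4-hourly readings already charted. If that is too much, the minimum is each study day's highest-VDI time point, with its MAP, doses and clock time. State in the SAP that worst VDI through day 10 is computed from these values. While editing, settle the window: the study summary's statistical considerations compare worst VDI over the first 6 days, whereas the study summary's primary safety variable and the SAP run through day 10.

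The cost is protocol, CRF and SAP wording plus extra chart abstraction, mainly for patients on vasopressors. No new measurement on patients is needed.

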Exclusion Criteria:	
 1. Subject unable to provide consent. 2. Patient, surrogate, or physician not committed to full support. 3. Malignant or other irreversible condition and estimated 28-day mortality $\geq 50\%$ 4. Moribund patient not expected to survive 48 hours (as defined by the primary medical team) from the start of study infusion 5. End-stage Liver Disease as defined by Child-Pugh Score > 9 6. Currently enrolled in, or having participated, in another study of an investigational compound within the last 30 days 7. Pregnant female or female who is breastfeeding 8. Allergy to L-citrulline or arginine or any citrulline- or arginine-containing product 9. Patient not otherwise suitable for the study in the opinion of any of the investigators 10. Requirement for intubation and invasive mechanical ventilation prior to study enrollment

Primary Clinical Efficacy Variables:	
The primary clinical efficacy variable is time to intubation event in hours from the start of study infusion.
 
Primary efficacy variables will be evaluated comparing intravenous L-citrulline vs. placebo in separate analyses.

Primary Biochemical Efficacy Variables:	
The primary biochemical efficacy variable is plasma levels of citrulline that are associated with primary and secondary clinical efficacy outcomes. It may serve as a surrogate marker for response.

Primary Safety Variable:	
Primary safety variable is hemodynamic status, specifically worst vasopressor dependency index through day 10.

Secondary Clinical Efficacy Variables:	
 1. All-cause hospital mortality 2. The requirement for intubation and invasive mechanical ventilation 3. Length of non-invasive mechanical ventilation in hours 4. Length of oxygen therapy in hours 5. Length of ICU stay in hours 6. Length of hospital stay in hours 7. Difference in proportion of patients intubated 8. Difference in proportion of patients intubated and on MV 9. Duration of mechanical ventilation from consent & post-infusion
Secondary Biochemical Efficacy Variables:	
 1. Plasma levels of citrulline and arginine at 2 hours, 12 hours, and study days 2, 4, 6, 8, 10. 2. Plasma NOx levels at 2 hours, 12 hours, and study days 2, 4, 6, 8, 10. 3. PK-PD analysis/modeling will enable dose proportionality (dose-response effect) determinations for a follow on confirmatory trial.

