or NO production (3) Labeled citrulline leaves the plasma and is metabolized by a full turn of the urea cycle before reentering as arginine, (4) Oral administration of ^{15}N -arginine results in a nearly five-fold greater recovery of tracer in $^{15}\text{NO}_3$ than when an equimolar amount of tracer is given intravenously, documenting significant splanchnic production of NO. Administration of IV citrulline significantly bypasses the splanchnic circulation, thus limiting the splanchnic production of NO. (5) About 15% of the plasma arginine turnover is associated with urea formation; only 1.2% is associated with NO production. As arginase is upregulated in sepsis, the amount of arginine available as substrate for NOS is further reduced. Although this may decrease NO production somewhat (likely limited due to the low percentage of arginine converted to NO normally), it also alters homeostasis by uncoupling NOS and limiting the amount of NO available to scavenge free radicals. Citrulline is resistant to arginase and our data demonstrate that citrulline administration produces a more consistent plasma level of arginine than arginine administration itself.

3.4 COVID-19 (SARS-CoV2) and Acute Hypoxemic Respiratory Failure Requiring Invasive Mechanical Ventilation

Although reports in the US literature on COVID-19 (SARS-CoV2) and critical illness is limited, a recent case series published in the New England Journal of Medicine detailed the clinical course of 24 critically ill adults with acute hypoxemic respiratory failure and confirmed COVID-19 infection (SARS-CoV2) in Seattle, Washington at 3 hospitals in the University of Washington health care system (106). The mean age was 64 +/- 18 years with a range of 23-97 years and 63% were male. Patients had symptoms an average of 7 days before hospital admission. Of the 24 patients, 18 or 75% required invasive mechanical ventilation but after exclusion of 3 patients who had "do not intubate" directives the percentage was to 18/21 or 86% requiring invasive mechanical ventilation. The median duration of invasive mechanical ventilation was 10 days (IQR 7-12) and overall mortality was 50% in this critically ill population.

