### **Missing Data**

Although every effort will be made to minimize the amount of missing data, some level of missing data will be unavoidable for a variety of reasons. In general, data may be missing due to subject's early withdrawal from study. Patients discontinuing early from the study and reasons for withdrawal will be summarized by treatment group to see if any biases in the analyses may have been created by any differences between groups. For the study of time-to-event endpoints, patients completing the study and not experiencing an event of interest are considered censored to the event. The impact of missingness will be minimized in the analysis of the primary endpoint by performing the analysis using Kaplan-Meier estimate, where participants will be censored at their last assessed time point. The procedures outlined below describing what will be done when data are missing may be refined during the blind review of the data.

For this Phase II study, missing data imputation will only be done for the primary and secondary biochemical outcomes (i.e., plasma levels of citrulline, arginine, ornithine, and NOx). For the analysis of other safety and secondary endpoints, no imputation will be done for missing values.

Missing biochemical data, it will be minimized operationally as we are setting up significant oversight on sample logistics. Nonetheless, given the longitudinal nature of data collection for biochemical measures, there exist the possibility of data truncation due to patient death.

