### ***Length of Oxygen Therapy in Hours***

### ***Length of Non-invasive Mechanical Ventilation***

We will provide median and range of length of non-invasive mechanical ventilation separately for each treatment group. There is an expectation that some patients will not require mechanical ventilation; therefore, overall duration of mechanical ventilation will be modeled with a zero-inflated Poisson model using consent and post-infusion start time for two separate analysis.

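### After day 11 the plan collects neither conventional oxygen nor the time oxygen stops, so length of oxygen therapy cannot be derived for patients with longer courses or discharged on oxygen

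*Protocol*

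**What the plan says.** Protocol 2.0 (Secondary Clinical Efficacy Variables, item 4) lists "Length of oxygen therapy in hours". SAP Table 1 and the SAP's list of secondary clinical endpoints repeat it. Protocol 4.2 and the SAP objectives also name oxygen therapy within a secondary objective.

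For day 12 to discharge, Protocol 7.2.2 lists "vital signs, hospital status, ICU status, and non-invasive and invasive ventilator settings". Appendix A has no row for oxygen therapy. Its nearest rows, "SaO2/ FiO2 ratio", PaO2, ABG, "Non-invasive ventilation status" and the matching invasive row, are marked for Days 1 to 11 and for nothing later.

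The SAP prints the heading "Length of Oxygen Therapy in Hours" and goes straight to the next heading, on non-invasive ventilation. The text there begins "We will provide median and range of length of non-invasive mechanical ventilation separately for each treatment group" and goes on to overall ventilation duration; oxygen is not mentioned. The SAP's Missing Data section adds: "For the analysis of other safety and secondary endpoints, no imputation will be done for missing values".

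**The concern.** A duration endpoint needs a start and a stop. The start is available, because Hour 0 is the start of infusion. An early stop is visible too: coming off all oxygen before day 10 ends study drug (Protocol 11.5) or participation (Protocol 5.1.2), and the daily SaO2/FiO2 entries run to Day 11. A late stop has no listed source.

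If the plan is followed as written, the endpoint is complete only for patients who recover early. Longer courses have no end point, and the SAP states no rule for them. The analyst would have to leave them out or truncate them by some unplanned convention. Length of course is what citrulline is meant to change, so the gap is not random with respect to outcome and may differ between arms.

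**Working it through.** **1. What is collected, and when**

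| Source | Days 1-11 | Day 12 to discharge | D28 and D60 calls |
|---|---|---|---|
| Protocol 7.2.2 text, ventilator settings | collected | collected, invasive and non-invasive | not listed |
| Appendix A, ventilation rows | marked | blank | blank |
| Appendix A, SaO2/FiO2, PaO2, ABG | marked | blank | blank |
| Vital signs, as defined in Protocol 7.1.2 | temperature, pulse, respiratory rate | the same | blank |
| Oxygen device, flow or stop time | no row | no row | no row |

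Appendix A gives the calls only hospital status, ICU status, concomitant medications and adverse events. Two findings follow. Conventional oxygen and the stop time have no listed source after day 11. Appendix A and 7.2.2 also disagree on whether ventilation data continue after day 11.

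**2. Inputs for the size**

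- Time to intubation: 3 days on placebo and 6.5 days as the citrulline target (Protocol 10.4).
- Ventilation, from the case series in Protocol 3.4: "The median duration of invasive mechanical ventilation was 10 days (IQR 7-12").

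**3. Check that the intubation inputs are read correctly**

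The plan states 81% power for a hazard ratio of 0.46 with 60 patients. The ratio is 3/6.5 = 0.46. Freedman's formula with an event in all 60 patients gives Φ(√60 × (1 − 0.46)/(1 + 0.46) − 1.96) = Φ(0.905) = 81.7%, which agrees. This power has no bearing on the oxygen endpoint; it only confirms the 3-day and 6.5-day readings.

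**4. Simple sums**

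Intubation at day 3 plus 7, 10 or 12 days of ventilation ends invasive support on day 10, 13 or 15. To be ventilated past day 11, such a patient needs more than 11 − 3 = 8 days. Interpolating linearly between the quartiles, P(duration > 8) = 1 − [0.25 + 0.25 × (8 − 7)/(10 − 7)] = 0.67.

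**5. Allowing intubation time to vary**

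Time to intubation T was taken as exponential. Duration D was taken as independent of T and fitted to quartiles 7/10/12 as Weibull, gamma, lognormal or normal. One million patients were simulated per case. Ranges are across the four shapes.

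| T | P(T + D > 11) | Same, among those intubated by day 11 |
|---|---|---|
| mean 3 days | 62.1-62.3% | 61.1-61.3% |
| median 3 days | 68.9-69.3% | 66.2-66.7% |
| mean 6.5 days | 75.9-76.6% | 70.5-71.4% |
| median 6.5 days | 81.6-82.4% | 73.3-74.5% |

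The middle column includes patients not yet intubated at day 11. At 6.5 days these are e^(−11/6.5) = 18% (mean) or 2^(−11/6.5) = 31% (median), so the right-hand column is the fairer one there. At 3 days they are only 3% or 8%, and the two columns together give 61-69%.

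A patient still ventilated after day 11 cannot have come off oxygen by day 11. Any oxygen after extubation comes on top.

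**The case against.** The strongest reply is that respiratory support is recorded after day 11. Section 7.2.2 carries ventilator settings to discharge, and Protocol 2.0 and 4.2 count high flow nasal cannula and BiPAP as non-invasive modalities. This stands. A reader might infer that nothing about oxygen or support is collected after day 11, and the text of 7.2.2 does not support that. It also means that the intubated patients counted above are followed while ventilated. The percentages show how many courses run past day 11, not how many patients go unobserved. What is lost is oxygen after extubation or step-down, low-flow oxygen in patients never intubated, oxygen after discharge, and the stop time itself.

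Other possible sources are weaker:

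- Protocol 12.1 makes chart abstraction a main data source, and 7.2.3 says the D28 and D60 follow-up will look again at the clinical outcomes. In-hospital stop times may well be in the chart, but neither section names oxygen, and an unlisted item need not be abstracted for everyone.
- Section 7.2.2 keeps the scheduled procedures going after study drug ends on Day 10, but its next paragraph sets a specific list from day 12, and that list omits conventional oxygen.
- The SAP's censoring rule covers time-to-event endpoints, and the SAP does not define this endpoint as one.

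A reader might also infer that citrulline patients would lose more data because later intubation pushes courses past day 11. That holds the share ever intubated fixed. The trial also aims to prevent intubation, which could shorten courses. The documents do not settle the direction.

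Finally, the ventilation figures come from 24 critically ill adults with mean age 64 and 50% mortality, whereas the trial enrols non-intubated floor patients aged 18-65. The figures therefore cannot be turned into a share of randomized patients.

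**Conclusion.** The gap is real and concerns data capture, not only missing detail in the SAP. Followed as written, the plan cannot yield length of oxygen therapy for anyone still on oxygen after day 11 or discharged on it. Missingness depends on the disease course, in an unknown direction. About 61-69% of intubated patients would still be ventilated after day 11 under the 3-day assumption. That figure rests on assumed distribution shapes, on independence of intubation time and duration, on ignoring deaths, and on a small, sicker series. The share of all randomized patients affected is unknown.

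It would go too far to say that the objective can never be addressed, since chart review might recover in-hospital stop times. The point is that nothing in the plan requires it. This is one of several secondary endpoints, and the primary analysis is untouched. It should be corrected because the remedy is cheap.

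**What to change.** - **Protocol 7.2.2 and Appendix A:** add oxygen support (device, and date and time of final stop) from day 12 to discharge. Reconcile the Appendix A ventilation rows, which end at Day 11, with 7.2.2, which continues them to discharge.
- **D28 call:** ask whether the patient is still on oxygen and, if not, the date it stopped.
- **SAP, oxygen therapy heading:** define the endpoint from Hour 0 to the final stop within a fixed window (day 28 would match the existing call) and name the analysis method. State one rule for patients still on oxygen when the window closes and one for deaths, so that an early death is not counted as short oxygen use.

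The cost is one chart-abstracted item, one question on a call already planned, and a short SAP paragraph. Stop dates after discharge would rest on recall and be known to the day, not the hour. Timing matters: the SAP plans database lock for September 2021 against a protocol version of June 2021, so a new call question may reach few patients. Chart abstraction can still cover in-hospital stops, but it should be done before the codes linking patients to data are destroyed (Protocol 11.5 and 12.2).
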